Timing (timing of each visit to be calculated based on date of randomisation visit)		Day -28 to Day -1	Day 1	Week 2	Week 4	Week 12 then every 12 weeks until 3 years (156 weeks)			Week 12, Week 24 and then every 24 weeks until 5 years (264 weeks) / yearly thereafter	Every 24 weeks until 5 years (264 weeks) / yearly thereafter	
Visit window	N/A	N/A	N/A	+/- 1 day	+/- 3 days	+/-7 days		+ 7 days	+/-7 days	+/-7 days	
Post study treatment discontinuation anti-cancer procedures and treatment								X	X	X	5.3.3
Subsequent response/progression data ^t										X (freq as per SoC)	
Survival Status										X ^u	5.1.3

- a) If screening assessments completed within 14 days they do not need to be repeated on Day 1 if patient's condition has not changed
- b) Treatment discontinuation visit to be performed only for the patients who prematurely discontinued treatment. For the patient who completed 3 years treatment (156 weeks), the last visit (Week 156) in treatment period will be considered as treatment discontinuation.
- c) As a minimum, telephone contact should be made with the patient 28 days (+7 days) following discontinuation of study drug
- d) Follow-up until disease recurrence visits to be performed for the patients who discontinue/completed treatment before disease recurrence
- e) Consent may be taken any time prior to 28 days window; Screening Part II period will start with first study-related assessment
- f) Mandatory: sufficient quantity for central confirmation of EGFR mutation status, retrospective T790M testing and for exploratory analyses
- g) Optional: tumour sample at disease recurrence
- h) Assessments to be completed pre-dose on the visit day

- i) All ECG data (with the exception of screening ECGs) will be collected digitally for the first year, standard ECGs will be performed thereafter; ECG is also to be performed in event of a cardiac AE
- j) MRI or contrast CT of brain must be done before randomisation if not performed prior to surgery. MRI/contrast CT scans of the brain must also be conducted at recurrence.

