6.1 Definition of adverse events

An adverse event is the development of an undesirable medical condition or the deterioration of a pre-existing medical condition following or during exposure to a pharmaceutical product, whether or not considered causally related to the product. An undesirable medical condition can be symptoms (e.g., nausea, chest pain), signs (e.g., tachycardia, enlarged liver) or the abnormal results of an investigation (e.g., laboratory findings, electrocardiogram). In clinical studies, an AE can include an undesirable medical condition occurring at any time, including run-in or washout periods, even if no study treatment has been administered.

The term AE is used to include both serious and non-serious AEs.

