6.3.3 Variables

The following variables will be collected for each AE:

- Adverse event (verbatim)
- The date when the AE started and stopped
- Changes in CTCAE grade (for skin reactions and diarrhoea only); maximum CTCAE grade for all other AEs
- Whether the AE is serious or not
- Investigator causality rating against the IP (yes or no)
- Action taken with regard to IP
- Adverse event caused patient's withdrawal from study (yes or no)
- Outcome

In addition, the following variables will be collected for SAEs:

- Date AE met criteria for serious SAE
- Date Investigator became aware of SAE
- Adverse event is serious due to
- Date of hospitalisation
- Date of discharge
- Probable cause of death
- Date of death
- Autopsy performed
- Causality assessment in relation to study procedure(s)
- Description of SAE

It is important to distinguish between serious and severe AEs. Severity is a measure of intensity whereas seriousness is defined by the criteria in Section [6.2](#). An AE of severe intensity need not necessarily be considered serious. For example, nausea that persists for several hours may be considered severe nausea, but not a SAE unless it meets the criteria shown in Section [6.2](#). On the other hand, a stroke that results in only a limited degree of

disability may be considered a mild stroke but would be a SAE when it satisfies the criteria shown in Section 6.2.

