8.4.2.1 Adverse events

Adverse events (both in terms of Medical Dictionary for Regulatory Activities [MedDRA] preferred terms and CTCAE grade) will be listed individually by patient.

Any AE occurring before treatment with study drug will be included in the data listings but will not be included in the summary tables of AEs.

Any AE occurring within 28 days of discontinuation of study drug (i.e., the last dose of AZD9291/placebo) and prior to the start of a new anti-cancer treatment will be included in the AE summaries. Any events in this period that occur after a patient has received further therapy for cancer (following discontinuation of study drug) will be flagged in the data listings. Please refer to Section [6.3.1](#).

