4.3.8.1. Adverse Events and Serious Adverse Events

All AEs, both in terms of MedDRA PT and CTCAE grade, will be summarised descriptively by count (n) and percentage (%) for each treatment arm. The latest MedDRA dictionary version will be used for coding. Missing coding terms should be listed and summarised as "Not coded".

The summary tables will include all AEs that occurred after the start of treatment up until the end of the 28-day follow-up period. For the IDMCs, the 28-day follow-up period will be defined as 28 days following discontinuation of study treatment. For the primary analysis and any subsequent analysis, the 28-day follow-up period will be defined as 28 days following discontinuation of study treatment and before starting subsequent cancer therapy. Any events in this period that occur after a patient has received further therapy for cancer (following discontinuation of study treatment) will be flagged in the data listings for all analyses.

All reported AEs will be listed along with the date of onset, date of resolution (if AE is resolved), investigator's assessment of CTCAE grade and relationship to study treatment. Frequencies and percentages of patients reporting each PT will be presented (i.e. multiple events per patient will not be accounted for apart from on the episode level summaries).

Summary information (the number and percent of patients by treatment) by SOC and PT will be tabulated for:

- All AEs
- All AEs causally related to study treatment
- AEs with CTCAE grade 3 or higher
- AEs with CTCAE grade 3 or higher, causally related to treatment
- AEs with outcome of death
- AEs with outcome of death causally related to treatment
- AEs leading to dose modification (interruptions and/or reductions)
- All SAEs
- All SAEs causally related to study treatment
- AEs leading to discontinuation of treatment
- AEs leading to discontinuation of treatment, causally related to treatment
- OAEs
- OAEs causally related to treatment

In addition, a truncated AE table of most common AEs, showing all events that occur in at least 5% of patients overall will be summarised by PT, by decreasing frequency. This cut-off may be modified after review of the data.

AEs will be assigned CTCAE grades and summaries of the number and percentage of patients will be provided by maximum reported CTCAE grade, SOC, PT and actual treatment group. Fluctuations observed in CTCAE grades during the study will be listed (where collected).

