AEs with outcome of death, SAEs, AEs leading to discontinuation of treatment, AEs causally related to treatment and OAEs will be listed.

Any AE occurring before study treatment will be included in the data listings but will not be included in the summary tables of AEs.

A separate summary of AEs occurring more than 28 days after discontinuation of AZD9291 (where reported) as well as those occurring prior to treatment will be produced. These events will not be included in other AE summaries.

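### The AE tables have no rule for an AE that starts before first dose and worsens on treatment; read by start date, it drops out of the main tables

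*SAP*

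**What the plan says.** SAP 4.3.8.1 sorts AEs into tables by timing. On inclusion it says: "The summary tables will include all AEs that occurred after the start of treatment up until the end of the 28-day follow-up period". For the primary and later analyses that period also ends when subsequent cancer therapy starts. On exclusion it says: "Any AE occurring before study treatment will be included in the data listings but will not be included in the summary tables of AEs". It then provides that a separate summary of AEs arising more than 28 days after discontinuation "as well as those occurring prior to treatment will be produced", and adds: "These events will not be included in other AE summaries".

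Protocol 8.4.2.1 carries the same rule: "Any AE occurring before treatment with study drug will be included in the data listings", but not in the summary tables.

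Neither document defines a treatment-emergent AE. Neither says where to count an AE that is already on record at first dose and later gets worse.

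**The concern.** An AE that was mild at first dose and afterwards became grade 3, became serious, or caused dosing to be interrupted or stopped is part of what happened on treatment. A rule that asks only whether the AE came before or after the start of treatment has no place for it.

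The tables at stake are those a reader relies on most: all AEs, grade 3 or higher, SAEs, dose modification and discontinuation. SAP 4.3.8.2 repeats the same set for AEs of special interest, so the gap carries over. The separate pre-treatment summary would show such an AE, but as something that happened before treatment.

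**Working it through.** No arithmetic applies, because the documents give no count of pre-dose AEs or of how many worsened. The check is to set the rules side by side.

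1. **Can an AE start before first dose?** Yes. Protocol 6.3.1 collects AEs from main consent. Protocol Table 1, footnote e, says "Consent may be taken any time prior to 28 days window". Screening Part II runs from Day -28 to Day -1, and Protocol 4.2 has the first dose taken within 2 days of randomisation. The interval from consent to first dose can therefore exceed four weeks.

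2. **What decides before or after?** SAP 4.3.8.1 speaks of when an AE occurred and does not name the start date. SAP 3.1.3.1, however, sets a partial AE start date to the first-dose date whenever it could fall there, and calls this the worst case. That is a worst case only if the start date governs whether the AE is counted. Sorting by start date is implied, not stated.

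3. **What does one AE record hold?** Protocol 6.3.3 takes a start and a stop date, grade changes for skin reactions and diarrhoea, and "maximum CTCAE grade for all other AEs". It also takes the action with study drug and, for SAEs, the date on which the AE became serious. A seriousness date separate from the start date makes sense only if an AE can evolve within one record. Protocol 6.9.2 and 6.9.4 place the grade changes on the AE form.

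4. **Apply the rule.** As an illustration, grade 1 fatigue starts after consent and before first dose. On treatment it reaches grade 3 and drug is interrupted. Kept as one record, it has a pre-dose start date, a maximum grade of 3 and an action with study drug. By start date it goes to the listings and the pre-treatment summary, and is absent from the grade 3 or higher and dose-modification tables.

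5. **Compare with the definition of an AE.** Protocol 6.1 includes "the deterioration of a pre-existing medical condition following or during exposure to a pharmaceutical product". The definition counts the deterioration; the table rule, read by start date, does not.

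6. **Which worsenings can be dated from data already collected?**
   - Skin reactions and diarrhoea: yes, from the grade changes. SAP 4.3.8.1 plans only to list these. Skin reactions also have form-based summaries in SAP 4.3.8.2.
   - AEs that become serious: yes, from the seriousness date.
   - AEs leading to action with study drug: yes. Such action cannot precede dosing, and SAP 3.3.5 shows dose changes recorded with dates and reasons.
   - All other AEs: no. Only a maximum grade is held, with no date attached.

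**The case against.** The strongest reply is that a deterioration on treatment would be entered as a new AE. Protocol 6.1 makes deterioration during exposure an AE in its own right, and Protocol 6.3.6 has aggravated examination findings reported as AEs. Entered that way, the event has an on-treatment start date and is tabulated. This stands as a possibility. No passage tells sites to open a new record, and the eCRF completion instructions are not among the documents, so counting would depend on site practice. A reader might infer that such events are certain to be missing from every main table; the documents do not go that far.

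A reader might also infer that the eCRF never shows when an AE worsened. That is wrong for skin reactions and diarrhoea, and Protocol 1.5 names rash and diarrhoea as the most frequent reactions. For these the gap lies only in the SAP's table rule.

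Other outputs recover part of the loss:
- SAEs and AEs leading to discontinuation are listed (SAP 4.3.8.1).
- Reasons for stopping treatment (SAP 4.3.1), deaths (4.3.8.3), and interruptions and reductions (4.3.8.4) are summarised.
- Laboratory shift tables (4.3.8.5) and the ECG and LVEF outlier summaries (4.3.8.8, 4.3.8.9) do not depend on AE onset.

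This also stands, but these outputs do not replace the AE tables for symptomatic events, and listings are not compared by arm.

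Finally, the exposed group is limited. Only AEs that start between main consent and first dose are affected, and Protocol 3.1 and 3.2 require prior-therapy toxicity to be grade 1 or lower at treatment start, apart from alopecia and grade 2 platinum neuropathy. That limits the number but does not remove the gap.

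**Conclusion.** The gap is real. Both documents exclude pre-treatment AEs from the main tables and neither provides for worsening after first dose. Followed as written, the rule can drop on-treatment worsening that Protocol 6.1 counts as an AE.

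This rests on two conditions: that start date decides inclusion, which SAP 3.1.3.1 implies, and that the worsening stays on the existing record, which Protocol 6.3.3 allows but nothing requires.

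The size is unknown. The ceiling is the number of patients with an AE starting between main consent and first dose, which the pre-treatment summary should show. A reader might infer that toxicity is understated mainly on osimertinib. Drug-related worsening would be expected to concentrate there, but unrelated worsening is lost in both arms and no figure in the documents supports a direction or an amount.

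The plan should be changed because the correction is cheap and mostly uses data already held, not because a large effect has been shown.

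**What to change.** In SAP 4.3.8.1 and Protocol 8.4.2.1 together, so that the two stay in agreement, define a treatment-emergent AE as one with:
- onset on or after first dose; or
- onset before first dose and any of the following on or after first dose, up to the end of the 28-day window (for the primary and later analyses, before subsequent cancer therapy): a recorded grade increase (skin reactions and diarrhoea), a date on which the AE met a seriousness criterion, or action taken with study drug because of the AE.

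For other AEs, state that worsening after first dose is entered as a new AE record in any further data collection. For data already collected, report pre-dose AEs that were ongoing at first dose and have a maximum grade of 3 or higher in a separate sensitivity table by arm. Do not add them to the main tables: the maximum grade carries no date, so a rule that counted every AE whose peak cannot be shown to predate dosing would bring in nearly every AE ongoing at first dose.

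The cost is a small derivation change, matching wording in the protocol and one additional table. The change can be applied to the later safety reporting foreseen in Protocol 8.7 and SAP Section 7.

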4.3.8.2. Adverse Events of Special Interest

Summary tables of AEs of special interest will be produced. The number (%) of patients experiencing any of the specified terms will be presented overall and by maximum CTCAE grade. Additional summaries of time to onset of first AE for each grouped term and each PT within it; time to onset of first CTCAE grade three or higher and duration of AEs of special interest will be produced. In addition, the summary tables in the AEs section listed above will be repeated for grouped AEs of special interest.

Life tables and prevalence plots for rash, diarrhoea, fatigue and stomatitis will also be produced.

The management of AEs of diarrhoea and rash will be summarised in terms of medication taken, dose modification and proportion of time on treatment.

Data collected on the specific eCRF for skin reactions will also be listed and summarised to further assess tolerability of specific events. Summaries will be by PT group for patient level and event level, overall, by effect and by CTCAE grade. The number of skin reactions per patient will also be summarised.

4.3.8.3. Deaths

A summary of deaths for the FAS will be provided with number and percentage of patients, categorised as:

- Related to disease under investigation,
- AE outcome=death,
- Both related to disease under investigation and with AE outcome=death,
- AE with outcome=death >28days after last treatment dose,
- Patients with unknown reason for death.

A corresponding listing will also be produced.

4.3.8.4. Exposure

Exposure will be summarised for safety analysis set. The following summaries will be produced:

- Summary of duration of exposure of study treatment including total exposure, actual exposure, and cumulative exposure over time (number and percentage for: ≥ 1 day, ≥ 6 months, ≥ 12 months, ≥ 18 months, ≥ 24 months, ≥ 30 months, ≥ 36 months)
- Summary of interruptions and reductions of study treatment

4.3.8.5. Laboratory Evaluations

All laboratory data recorded in the eCRF will be listed. If any additional analytes to those in [Table 4](#) are also recorded, then these will be listed only.

All values will be classified as low (below range), normal (within range) and high (above range) based on project-specific reference ranges. As applicable, values will be converted to standard units and will be graded using CTCAE v4.0.

For the primary analysis and any subsequent analysis only data collected before starting further cancer therapy will be summarised.

For clinical chemistry and haematology, shift tables will present movements in and out of reference range or, if applicable, CTCAE grade changes from baseline to the maximum/minimum value on treatment will be provided. Corresponding shift tables (“Negative”, “Trace”, “Positive”, “0”, “+”, “++”, “+++”) will be produced for urinalysis.

Plots of both the maximum post-baseline alanine aminotransferase (ALT) and aspartate aminotransferase (AST) versus the maximum post-baseline total bilirubin, expressed as multiples of their upper limit of reference range will be produced. Box plots of absolute values and change from baseline for all haematology and clinical chemistry parameters will also be presented.

A pregnancy test will also be performed at screening only for women of child-bearing potential.

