- k) In the rare case where a patient is intolerant of the contrast medium, the preferred imaging would be CT chest without contrast and MRI abdomen with contrast however non contrast abdominal CT will also be accepted. All recurrences on study need to be confirmed with imaging of the chest and abdomen (including liver and adrenal glands). The imaging method used at baseline (CT or MRI) must be used at each subsequent follow-up assessment. MRI/contrast CT scans of the brain must be conducted at recurrence.
- l) Baseline scans within 28 days of first dose
- m) Required only if suspicious signs/symptoms are not covered by CT of chest and abdomen (including liver and adrenal glands) at baseline and follow-up
- n) If for any reason a sample is not drawn prior to dosing, it may be taken at any visit until the last study visit
- o) Plasma samples 10ml prior to first randomised dose on Day 1; 20-30 ml at every 12 weeks visits. If patient discontinues study treatment prior to disease recurrence, samples should continue to be collected in accordance with the scan schedule until disease recurrence is noted.
- p) Blood sampling at 4 weeks, 24 weeks, 48 weeks, 96 weeks after randomisation. Blood draw to occur 3 times at each visit at following time points: pre-dose, between 0,5 -1,5h post dose, between 2-4 h post dose. 96 week PK sample post IDMC7 analysis will not be collected.
- q) SF 36 at 12 weeks, 24 weeks and then every 24 weeks relative to randomisation (\pm 7 days) until disease recurrence
- r) Patients will be asked about any health resource use between visits (i.e., excluding routine follow-up clinic visits associated with the clinical trial but including both planned and unplanned admissions) at every scheduled visit during the study.
- s) AEs ongoing at treatment discontinuation to be followed through to resolution; thereafter, only SAEs /concomitant medications for SAEs considered related to IP and study procedures to be recorded in eCRF
- t) Investigator assessment of response/progression to be collected
- u) To establish survival status patient will be contacted in the week following date of DCO for IDMC and in the two weeks following date of DCO for primary analysis and subsequent analyses.

Table 2 Study Plan for OS period - post final DFS analysis and up to final OS analysis

	Treatment Period	Post-Treatment			Protocol Section
		Treatment discontinuation ^a	28 day Follow up ^b	Follow up for survival	
Visit	On treatment				

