4.2 Treatment period

Patients will be randomised at Visit Day1 and receive either AZD9291 or matching placebo. Patients will take the first dose of study drug within 2 days of randomisation and will continue treatment until recurrence of disease, treatment discontinuation criterion is met or treatment is completed. The treatment duration period is 3 years (156 weeks), except for patients who receive open-label osimertinib after recurrence and continue until subsequent progression or another one of the situations described in Section 3.10.

The assessments required during the treatment period are detailed in the Study Plan [\(Table 1\)](#).

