5.2 Safety assessments

5.2.1 Laboratory safety assessments

Blood and urine samples for determination of clinical chemistry, haematology, and urinalysis will be taken at the times indicated in the Study Plan [Table 1](#). Additional safety samples may be collected if clinically indicated at the discretion of the Investigator. The date and results (values, units, and reference ranges) will be recorded on the appropriate eCRF. The clinical chemistry, haematology, and urinalysis will be performed at a local laboratory at or near to the Investigator site. If clinical chemistry, haematology, and urinalysis assessments have been performed within 14 days pre-randomisation, they do not have to be repeated prior to commencing treatment on randomisation visit Day 1 if the patient's condition has not changed (i.e., no new treatment during this period of time, no new complication, or aggravation). Sample tubes and sample sizes may vary depending on laboratory method used and routine practice at the site. The number of samples/blood volumes is therefore subject to site-specific change.

The following laboratory variables will be measured (3).

Table 4 Laboratory safety variables

Clinical chemistry	Haematology
S/P-Albumin	B-Haemoglobin
S/P-ALT	B-Leukocyte
S/P-AST	B-Haematocrit
S/P-Alkaline phosphatase	B-RBC count
S/P-Bilirubin, total	B-Absolute leukocyte differential count:

Clinical chemistry	Haematology
S/P-Calcium, total	Neutrophils
S/P-Creatinine	Lymphocytes
S/P-Glucose (fasting, on PK days only) ^a	Monocytes
S/P-LDH ^b	Basophils
S/P-HbA1C	Eosinophils
S/P-Magnesium	B-Platelet count
S/P-Potassium	B-Reticulocytes
S/P-Sodium	
S/P-Urea nitrogen/BUN	
Urinalysis	
	U-Glucose
	U-Protein
	U-Blood

ALT=alanine aminotransferase; AST=aspartate aminotransferase; B=blood; BUN=blood urea nitrogen;
HbA1C=haemoglobin A1C; LDH=lactate dehydrogenase; P=plasma; RBC=red blood cells; U=urine;
S=serum.

^a Patients will be required to fast (water only) for at least 8 hours prior to the collection of a fasting glucose sample required on PK days. Random glucose sample will be collected on non-PK days.

^b LDH is an additional variable collected at Screening visit only.

Additionally, at the Screening Visit, a pregnancy test (blood or urine tests are acceptable based on the site's standard clinical practice) will be collected from all women of child-bearing potential only.

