5.4 Pharmacokinetics

5.4.1 Collection of samples

Pharmacokinetics blood sampling (2 mL each) will be performed for all patients at pre-dose, 0.5 to 1.5 hours, and 2 to 4 hours post dose on Week 4, Week 24, Week 48 and Week 96. Week 96 PK sample post IDMC7 analysis will not be collected. Dose time information must be collected on both the day of PK sampling (to determine the exact times of the post-dose PK

samples), and the day immediately prior to PK sampling (to allow the pre-dose PK sample to be used). The date and time of collection of each sample and the date and time of dose will be recorded. Samples will be collected, labelled, stored, and shipped as detailed in the Laboratory Manual.

Placebo samples will not be analysed unless specified. No further PK samples will be collected from patients who receive for open-label osimertinib.

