3.3.6. Laboratory Safety Variables

Table 4 below shows the laboratory safety variables that will be summarised.

Table 4 Laboratory safety variables

Clinical chemistry (Serum [S] / Plasma [P])	Hematology (Blood [B])	Urinalysis (Urine [U])
S/P-Albumin	B-Haemoglobin	U-Glucose
S/P-ALT	B-Leukocyte	U-Protein
S/P-AST	B-Haematocrit	U-Blood
S/P-Alkaline phosphatase	B-Red blood cells (RBC) count	
S/P-Bilirubin, total	B-Absolute leukocyte differential count:	
S/P-Calcium, total	Neutrophils	
S/P-Creatinine	Lymphocytes	
Creatinine Clearance [†]	Monocytes	
S/P-Glucose (fasting, on PK days only) [‡]	Basophils	
S/P-Lactate dehydrogenase (LDH) [§]	Eosinophils	
S/P-Magnesium	B-Platelet count	

[†] Creatinine clearance will be derived using the method of Cockcroft and Gault (Cockcroft & Gault, 1976).

[‡] Patients will be required to fast (water only) for at least eight hours prior to the collection of a fasting glucose sample required on PK days. Random glucose sample will be collected on non-PK days.

[§] LDH is an additional variable collected at Screening only.

Clinical chemistry (Serum [S] / Plasma [P])	Hematology (Blood [B])	Urinalysis (Urine [U])
S/P-Potassium S/P-Sodium	B-Reticulocytes Haemoglobin A1C (HbA1C)	
S/P-Urea nitrogen/Blood urea nitrogen (BUN)		

Corrected calcium will be derived during creation of the reporting database using the following formula:

$$\text{Corrected calcium (mmol/L)} = \text{Total calcium (mmol/L)} + ([40 - \text{albumin (g/L)}] * 0.02)$$

Creatinine clearance will be derived during creation of the reporting database according to the Cockcroft-Gault formula:

$$\text{Creatinine clearance (mL/min)} = ([140 - \text{age at randomization}] * \text{weight (kg)} [* 0.85 \text{ if subject is female}]) / (72 * \text{serum creatinine (mg/dL)})$$

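### On-treatment glucose is fasting at up to four visits but baseline glucose is random; the SAP analyses it as one parameter, so changes at those visits compare unlike samples

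*SAP*

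**What the plan says.** Protocol 5.2.1 (Table 4) lists the variable as "S/P-Glucose (fasting, on PK days only" and a footnote makes it random on other days. SAP 3.3.6 (Table 4) carries the same single row and footnote: "Random glucose sample will be collected on non-PK days".

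PK days are fixed in two places. Protocol section 4, Table 1, footnote p reads "Blood sampling at 4 weeks, 24 weeks, 48 weeks, 96 weeks after randomisation", and Protocol 5.4.1 gives the same schedule: "post dose on Week 4, Week 24, Week 48 and Week 96". Section 5.4.1 adds a later change: "Week 96 PK sample post IDMC7 analysis will not be collected".

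Dosing begins before any of these days (Protocol 4.2): "Patients will take the first dose of study drug within 2 days of randomisation". Chemistry is drawn at screening and again on Day 1 under the Table 1 footnote "Assessments to be completed pre-dose on the visit day". The Day 1 draw may be omitted if screening results are no more than 14 days old.

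SAP 4.2.1 takes the last observation before first dose as the safety baseline. SAP 4.3.8.5 then plans "Box plots of absolute values and change from baseline for all haematology and clinical chemistry parameters", and shifts from baseline to the maximum or minimum on treatment. SAP 3.1.2 takes that maximum or minimum over all on-treatment values. No SAP text separates fasting from random glucose. SAP section 6 moves HbA1c to another column of Table 4 but does not mention fasting state.

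**The concern.** A change from baseline can be read as a treatment or time effect only if the two samples were taken under the same conditions. For glucose, every fasting sample falls after treatment starts and no fasting sample is scheduled before it. At PK visits the planned change therefore contains the difference between fasting and random glucose as well as any real change.

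The stake is modest but real. Under Protocol 6.3.6, worsening of a protocol-mandated laboratory value is reported as an adverse event only if it meets a seriousness criterion or leads to discontinuation; accompanying signs or symptoms are reported in their own right. A symptom-free, non-serious rise in glucose would therefore show up mainly in the laboratory outputs. An artificial fall at the PK visits could hide part of such a rise when one arm is read on its own.

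**Working it through.** The plan states no figure for this point, so the check rebuilds the schedule and applies the SAP rules to it.

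**Draws before first dose** (Protocol Table 1): screening and Day 1. Neither is a PK day, so 0 of 2 are fasting.

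**On-treatment draws to week 156** (Protocol Table 1): weeks 2 and 4, then every 12 weeks from week 12 to week 156, which is 156/12 = 13 visits. Total 2 + 13 = 15.

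| | Fasting | Random | Share fasting |
|---|---|---|---|
| Week 96 PK sample taken | 4 (weeks 4, 24, 48, 96) | 15 − 4 = 11 | 4/15 = 27% |
| Week 96 PK sample dropped after IDMC7 | 3 (weeks 4, 24, 48) | 15 − 3 = 12 | 3/15 = 20% |

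**Cross-check against Protocol Table 5.** Safety blood: 15 mL × (4 + 13 + 1) = 270 mL. PK blood: 3 × 2 mL × 1 + 3 × 2 mL × 3 = 6 + 18 = 24 mL. Both match the printed subtotals, and the table shows no PK blood at screening or Day 1.

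**Effect on change from baseline.** Let random glucose average *d* above fasting glucose, and let the drug add *t* in the active arm.

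- PK visit, placebo: fasting − random = −*d*
- PK visit, active: *t* − *d*
- PK visit, difference between arms: (*t* − *d*) − (−*d*) = *t*
- Other visits: 0 on placebo and *t* on active, because both samples are random

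The documents give no value for *d*. As an assumption, *d* = 0.3, 0.5, 1.0 or 1.5 mmol/L gives a mean change at PK visits of −0.3, −0.5, −1.0 or −1.5 mmol/L with no drug effect. A true rise equal to *d* would show as zero change within the active arm. The difference between arms keeps *t*, provided *d* is the same in both.

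**Effect on the shift tables.** The maximum and minimum are taken over fasting and random values together. With *d* above zero, fasting values tend to supply the minimum, which is then set against a random baseline. The maximum tends to be a random value, set against a random baseline.

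**Week 96.** Samples taken after IDMC7 are random and earlier ones fasting, so one nominal visit holds both states across patients.

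**The case against.** Several points on the other side stand.

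- **Most changes are matched.** At 11 of the 15 visits a random value is compared with a random baseline.
- **The arms share the artefact.** Both follow the same blinded schedule, so the within-arm change is distorted more than the contrast between arms.
- **The SAP could be programmed differently.** If fasting glucose were handled as its own parameter it would have no baseline, and under SAP 3.1.3 nothing would be imputed, so no false fall would appear. But the SAP does not specify that split, and the change and shift outputs promised for all chemistry parameters could not then be produced for fasting glucose.
- **Random means uncontrolled, not fed.** Some baselines may happen to have been fasted, which would make *d* smaller.
- **The consequence is limited.** SAP 2.1.2 says safety data are not formally analysed, and all laboratory values are listed.

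SAP 4.3.9 refers to PK concentrations on Day 1 of cycles 1 and 3, which might suggest a fasting sample on Day 1. The protocol schedules no PK draw on Day 1, so this does not supply a fasting baseline.

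Three stronger readings are tempting, and the documents do not support them.

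1. A reader might infer that the outputs can neither show nor exclude hyperglycaemia. HbA1c and urine glucose are both in SAP Table 4 and already receive the planned outputs, and comparisons between arms at a visit remain usable.
2. A reader might infer that pooling makes glucose appear to rise because of fasting state. The maximum of many draws tends to exceed a single baseline for any analyte under the general rule in SAP 3.1.2, and for glucose that maximum is usually a random value against a random baseline.
3. A reader might infer a spurious difference between arms, because patients who stay on treatment longer contribute more draws, and all draws after week 96 are random. Dependence of a maximum on exposure applies to every laboratory variable, and the documents give no basis for a size specific to glucose.

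**Conclusion.** The point holds in a limited form. The mismatch affects changes at up to four PK visits per patient and the shift tables, most clearly the shift to the minimum. It does not systematically affect change at the other visits.

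The downward direction assumes that random glucose averages above fasting glucose; its size is that unknown difference, illustrated here as 0.3 to 1.5 mmol/L. The existence of the mismatch depends on neither assumption, only on the sampling schedule and the SAP baseline rule. These are descriptive safety outputs and no efficacy test is touched. It is a minor but worthwhile correction.

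**What to change.** In SAP 3.3.6 and 4.3.8.5, define glucose as two parameters.

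- **Random glucose:** change and shift from the random baseline to random on-treatment values only.
- **Fasting glucose:** absolute values and category by arm at the PK visits, with no change or shift from baseline.
- **Fasting status:** assign it from whether a PK sample was actually collected from that patient on that day, not from the nominal visit or analysis window. Week 96 samples after IDMC7, and unscheduled samples that fall in a PK visit's window, are then treated as random. Protocol 5.4.1 has PK blood drawn from all patients with collection dates recorded, so the flag can be set in both arms.
- **Glycaemic change from baseline:** refer the reader to the HbA1c outputs, which are already planned.

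The cost is a few lines of SAP wording and one derived flag; no new data are needed. The downside is fewer values in each glucose table.
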